## **Intervention Delivery**

Evidence recommends a minimum duration of 12 weeks for a HIT protocol to promote favorable changes in blood pressure and anthropometric measurements of obesity. However, a 6-week intervention was selected, as a minimum of 13 sessions (0.16 work/rest ratio) is sufficient to elicit moderate improvements in VO2 max in sedentary individuals. Additionally, there is still ambiguity regarding the optimal work-to-rest ratio when designing HIT interventions, particularly in populations with varied age, baseline fitness, and training experience. Therefore, longer duration HIT models (1-4 min) were deemed unsuitable for our target population. Furthermore, minigames (such as the current exergame) have short life spans, where adherence to a longer intervention (eg, 12 weeks) may diminish over time and influence health outcomes. This was evident from a 12-week pilot study (unpublished data) using an exergame in the same population that saw attendance drop from 53% during week 2 to 16% during week 12.

Participants allocated to the intervention group were invited to attend three sessions of exergaming per week. At the beginning of the exergaming session, participants were required to complete a 6-min structured warm-up consisting of a series of exercises on a 210 mm step until both participants reached ~70% HRmax. Session workloads with volumetric progression were set automatically once the user's identifying information was entered. The session workloads were 120s-, 150-s, and 180-s of work during weeks 1 and 2, weeks 3 and 4, and weeks 5 and 6, respectively.

To avoid staleness, the repetition lengths (10, 20, or 30-s) were randomly selected at the beginning of each round. We set the work-to-rest ratio at 1:4, and thus, the respective repetitions were followed by 40, 80, or 120-s of active recovery. Participants were instructed to perform the repetitions at an intensity  $\geq$ 85% HRmax. Each exergaming session took approximately 30 to 40 min to complete, including equipment set-up, warm-up with additional enjoyment, and task immersion questionnaires upon completion of the HIT bouts (not reported here). Heart rate responses were taken within repetitions and therefore, did not include any of the recovery period. This, therefore, avoided an overestimation of physiological load, which can occur when heart rate continues to rise after exercise cessation.

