### **Statistical Analysis**

Exergaming session attendance was calculated using descriptive statistics. Training data (heart rate [repetition mean and peak], rating of perceived exertion [RPE]) were analyzed using a mixed linear model with a random intercept (Statistical Package for the Social Sciences [SPSS] version 23 [IBM Corp]).

This approach enabled us to calculate (1) the within-participant variability in the training dose, expressed as an SD; (2) the effect of HIT repetition duration (entered as a fixed effect) on heart rate and RPE; and (3) the change in heart rate and RPE across the 6-week HIT intervention, with session number (1-18) entered as a fixed effect. A priori, we defined a minimal practically important difference (MPID) in training heart rates as two percentage points, given that when training at high-intensity, this difference influences the adaptive response.

The MPID for RPE was set at one arbitrary unit (AU) on the Borg CR10 Scale, representing a full increment change on the scale. Inferences were then based on the disposition of the 90% confidence limits (CLs) for the mean difference to these MPID; the probability (percent chances) that differences in heart rate and RPE between HIT repetitions of different durations or across the 6-week intervention were substantial (>2 percentage points, >1 AU) or trivial was calculated as per the magnitude-based inference approach described by Batterham and Hopkins, an approach that has been advocated within user research.

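### The session-number effect on heart rate and RPE mixes any change in repetition intensity with the larger share of late repetitions in later, longer sessions

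*Combined protocol and SAP*

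**What the plan says.** Under Intervention Delivery, volume is progressed on a common schedule: "Session workloads with volumetric progression were set automatically once the user's identifying information was entered". The steps are given next: "The session workloads were 120s-, 150-s, and 180-s of work during weeks 1 and 2, weeks 3 and 4, and weeks 5 and 6, respectively". Three sessions a week are offered ("Participants allocated to the intervention group were invited to attend three sessions of exergaming per week"), so 3 x 6 = 18 sessions, six at each workload. Within a session, "the repetition lengths (10, 20, or 30-s) were randomly selected at the beginning of each round", with recovery at four times the repetition length and an instruction to work at 85% HRmax or above. Heart rate is taken inside repetitions only.

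Under Statistical Analysis, repetition mean and peak heart rate, and RPE, go into a mixed linear model with a random intercept. Two fixed effects are named: "the effect of HIT repetition duration (entered as a fixed effect) on heart rate and RPE", and, for change over time, "the change in heart rate and RPE across the 6-week HIT intervention, with session number (1-18) entered as a fixed effect". Differences are placed against the MPIDs (2 points, 1 AU) through 90% confidence limits and percent chances. No term for repetition order, accumulated work or workload block is described.

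**The concern.** The variable that carries time also carries volume. A 180-s session contains every stage of a 120-s session plus a further 60 s of work at the end. If heart rate or RPE climbs as work accumulates, the average over a late session is higher than over an early one, even when a repetition at a given point in the session is performed exactly as before.

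The session effect would then show a rise that reflects only where the repetitions fall. Equally, it could conceal a real fall in effort per repetition and return a trivial result. A shift smaller than the MPID still moves the percent chances and can change the label attached to them. Control participants do no exergaming sessions, so they cannot separate the two sources.

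**Working it through.** The plan states no figure on this point beyond the 18 sessions, which agree with 3 x 6. The check has four steps.

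**1. Session number against programmed work.** Take s = 1 to 18 and W = 120, 150, 180 s, six sessions each. The block means of s are 3.5, 9.5 and 15.5.
- Sxy = 6(-6)(-30) + 6(6)(30) = 2160; Sxx = 484.5; Syy = 12 x 900 = 10,800.
- r = 2160/√(484.5 x 10,800) = 0.944.
- Fitted slope = 2160/484.5 = 4.458 s per session, or 17 x 4.458 = 75.8 s from session 1 to 18. A straight line through the three steps thus stretches the 60-s difference by 75.8/60 = 1.263.

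**2. How much later repetitions fall.** With equal lengths L, mean work already done before a repetition is (W - L)/2.

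| L | W = 120 | W = 150 | W = 180 |
|---|---|---|---|
| 10 s | 55 | 70 | 85 |
| 20 s | 50 | 65 | 80 |
| 30 s | 45 | 60 | 75 |

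The rise is 30 s at every length, so neither random lengths nor the duration term removes it. With lengths drawn at random per repetition and full attendance, simulation gives mean positions of about 3.8, 4.5 and 5.3, a shift of 1.5 positions.

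**3. Effect on the session term, with no true change over the weeks.** The documents give no drift, so these values are assumptions. By hand, a linear drift of d points per repetition gives 1.5 x 1.263 x d = 1.9d. Simulated schedules, fitted by least squares on session number (linear) and duration, agree:

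| Assumed drift in %HRmax | Spurious change, session 1 to 18 |
|---|---|
| linear, 0.5 per repetition | 0.95 |
| linear, 1 per repetition | 1.9 |
| linear, 2 per repetition | 3.8 |
| 1 per repetition, flat from the 4th | about 0.4 |
| 2 per repetition, flat from the 3rd | 0.38 |
| 2 per repetition, flat from the 4th | 0.76 |
| exponential rise of 8 points, constant 2 repetitions | 1.13 |

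The MPID is 2. If session is fitted as 18 categories, the first-to-last contrast is 1.5d: 0.75, 1.5 or 3.0 for the linear cases. Expressed by accumulated work, the spurious change is 30 x 1.263 = 37.9 s of prior work. It reaches 2 points when heart rate rises 2 x 120/37.9 = 6.3 points per 120 s, and 1 AU when RPE rises about 3.2 AU per 120 s.

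**4. What an adjustment does.** At repetition level, session number and position correlate only about 0.22, so they can be separated.
- One linear position term removes the bias under linear drift and raises the SE of the session slope by about 3%. Under the plateau and exponential shapes it over-corrects, by about -0.4 to -0.6 points.
- Categorical position leaves zero under every shape in the table.
- Using repetitions that start within the first 120 s of work leaves about zero.

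**The case against.** The strongest reply is that the session effect is right for its purpose. The trial sets out to assess whether the game delivers the intended stimulus (Participants section). Progression is part of that stimulus, so the change including later repetitions describes what participants received. The heart-rate MPID fits this reading: it is a dose threshold, and 2 points more intensity matters whatever produced it. This stands. A reader might infer that the plan presents the session effect as a training adaptation. It does not; it speaks only of change across the intervention. What the reply leaves open is whether intensity per repetition, which has its own 85% instruction, held up over the weeks. The session effect alone cannot answer that.

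The second reply is that the bias may be small. This also stands. Of the linear values only 2 points per repetition passes the MPID. Over about 9.3 repetitions in weeks 5 and 6 that is a rise of 2 x 8.3 = 16.6 points, which from 85% would end above 100% of HRmax. A warm-up to about 70%, recovery at 1:4 and live heart-rate feedback make an early plateau at least as plausible.

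Two further inferences should be resisted.
- The 0.94 correlation is with the session total; it does not make the effects inseparable at repetition level.
- The 10-, 20- and 30-s contrast might seem biased too, because short repetitions could fill the end of a session. That needs lengths to be fitted to the session total, which the documents do not say. With unfitted lengths the false 30-s minus 10-s difference is 0.02 points at a drift of 1 point per repetition.

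**Conclusion.** The point holds in limited form. As described, the session effect combines change in repetition intensity with a shift of about 1.5 positions towards late repetitions, and nothing in the described model separates them. The direction is upward if heart rate or RPE rises within sessions.

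The size cannot be established from the documents: about 0.4 to 1.1 points under early plateaus and 0.95 to 3.8 under the linear drifts, against an MPID of 2. A reader might conclude that the bias exceeds the MPID; that holds only for fairly steep, sustained drift.

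These figures assume full attendance, session number entered linearly and in the same model as duration, and lengths drawn independently. The text does not settle those model details, or whether session number counts scheduled or attended sessions. Nor does it say whether RPE was rated per repetition or per session. If per session, rising total work is confounded with it directly and repetition position cannot adjust it. The point concerns a process measure in an exploratory trial and does not touch the between-group health outcomes.

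**What to change.** 1. Keep the unadjusted session effect and label it as change in load as delivered, including the programmed rise in volume.
2. Add a comparison at equal work for repetition mean and peak heart rate. Either enter repetition position as a categorical fixed effect beside duration and session number, or restrict the analysis to repetitions that start within the first 120 s of work, which every session contains. Do not use a single linear position term, which over-corrects if heart rate levels off. Do not substitute total session work: its variance inflation with session number is 1/(1 - 0.944²), about 9.2, which makes the SE of the session slope about three times as large.
3. Base any statement that repetition intensity rose, fell or was maintained on the equal-work comparison.
4. State how RPE was recorded. If per repetition, treat it in the same way; if per session, report it as change under rising workload.
5. State whether session number is linear or categorical, and scheduled or attended.

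The cost is one additional analysis of the repetition heart-rate data, which needs the order of repetitions within each session, and a slightly larger SE: about 3% with a linear position term, and somewhat more with categories or with the restriction, which discards the later repetitions.

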## Participants

We conducted a 6-week exploratory controlled trial designed to assess the fidelity of the game in terms of delivering the intended training stimulus and to examine the effect of the intervention on selected health outcomes. As appropriate for an exploratory trial, we did not conduct formal sample size estimation a priori, rather the CIs would be used to inform future trials. Men are commonly referred to as a hard-to-reach population to engage in health promotion activities, where a targeted recruitment approach at locations predominantly attended by men may facilitate uptake of participants. Therefore, to maximize recruitment within our intended population, relevant gatekeepers were approached at institutions positioned within regions of social deprivation. Thus, two settings used for recruitment and the trials were a social club and mosque, both situated within deprived regions of Middlesbrough, United Kingdom (TS1 and TS4). Recruitment in the social club relied heavily on the gatekeeper (club secretary), whereas uptake of South Asian men from a local mosque was more straightforward; all 9 mosque participants were recruited from a single demonstration (and we had similar experiences in previous iterations). Presumably, the intervention was culturally salient in this population; the North of England has developed some famous prominent Muslim boxers (eg, Amir Kahn and Naseem Hamed) in recent years, and when delivered in the safe form, was acceptable to the respected leaders of the religious groups (ie, the Imam of the mosque). A total of 24 males were recruited into the trial using relevant gatekeepers at institutions positioned within regions of social deprivation. Two recruitment drives (October 2014 and February 2015) took place, and these involved live demonstrations of the technology followed by word-ofmouth and snowballing approaches. The exergaming system was important in this recruitment process because it provided something tangible and interesting to engage potential participants.

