Inclusion criteria were deliberately broad to maximize recruitment, that is, apparently healthy, as defined by ACSM guidelines and in the age range of 18 to 55 years. Participants were given a £15 shopping voucher upon completion of follow-up measures (week 7) irrespective of their adherence to the intervention protocol or group allocation. The intervention took place from November 2014 to December 2014 (social club) and March 2015 to April 2015 (mosque). Postcode data were analyzed to match against indices of multiple deprivation in lower-layer super output areas to check whether the cohort fell within our target population.

A third-party minimization process using baseline measures of age, waist circumference, and predicted maximum oxygen consumption  $(VO_2 \text{ max})$  was used to remove bias in group allocation. The control group was instructed to maintain their current physical activity levels and inform the researchers should any changes arise during the intervention

To explore perceptions of the exergame and the HIT regime, semistructured interviews were conducted with 5 intervention participants following the 6-week training period, which were analyzed semantically. The study was approved by the ethics committee of Teesside University, United Kingdom, and written informed consent was obtained from all participants.

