These percent chances were qualified via probabilistic terms assigned using the following scale: 25 to 75%, possibly; 75 to 95%, likely; 95 to 99.5%, very likely; and >99.5%, most likely. To determine the magnitude of the within-participant variability in our training heart rate and RPE, the values were doubled and then interpreted against aforementioned MPID. All training data effects were evaluated mechanistically, whereby if the 90% CL overlapped the thresholds for the smallest worthwhile positive and negative effects, the effect was deemed unclear. The effect of HIT on our outcome measures was determined using a custom-made spreadsheet, with the baseline value of the dependent variable used as a covariate to control for baseline between-group imbalances. Following this, standardized thresholds for small, moderate, and large changes (0.2, 0.6, and 1.2, respectively) derived from between-subject SDs of the baseline values were used to assess the magnitude of all effects, with magnitude-based inferences subsequently applied. Here, all inferences were categorized as clinical, with the default probabilities for declaring an effect clinically beneficial being <0.5% (most unlikely) for harm and >25% (possibly) for benefit.

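### Allocation was minimised on three baseline factors, but the health-outcome analysis adjusts only for own baseline, so its intervals are conservative if the omitted factors are prognostic

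*Combined protocol and SAP*

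**What the plan says.** The Participants section describes the allocation: "A third-party minimization process using baseline measures of age, waist circumference, and predicted maximum oxygen consumption". The same section says "A total of 24 males were recruited into the trial", reports no prior sample size estimation, and gives the purpose of the intervals: "rather the CIs would be used to inform future trials".

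The Statistical Analysis section covers the health outcomes in one sentence. The estimates come from a purpose-built spreadsheet, and the only adjustment described is this: "with the baseline value of the dependent variable used as a covariate to control for baseline between-group imbalances". No further covariate is named in the text supplied. The results then go through a clinical rule, with "default probabilities for declaring an effect clinically beneficial being <0.5% (most unlikely) for harm and >25% (possibly) for benefit".

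The 90% level is stated in the paragraph on training data: "Inferences were then based on the disposition of the 90% confidence limits (CLs) for the mean difference to these MPID". For the health outcomes it applies by implication.

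**The concern.** Minimisation makes the arms alike on its factors. If a factor predicts the outcome, that likeness reduces the true sampling variance of the group difference. A model that leaves the factor out does not register the reduction: the factor's contribution stays in the residual variance, and the standard error is too large. Adjusting for own baseline removes only what own baseline explains.

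| Outcome | In the model | Minimisation factors left out |
|---|---|---|
| Blood pressure | own baseline | age, waist, predicted VO2 max |
| Waist | own baseline (a factor) | age, predicted VO2 max |
| Predicted VO2 max | own baseline (a factor) | age, waist |

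Interval width is a main product of this trial, because later trials are to be planned from it. The same standard errors feed the harm and benefit probabilities.

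**Working it through.** The plan gives no figure to reproduce. The check asks how far coverage departs from 90%, and what adjustment costs.

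**Inputs.** From the documents: n = 24, the three minimisation factors, own baseline as sole covariate, 90% level (by implication). Assumed: arms of about 12 and 12; minimisation details (continuous or categorised factors, random element), which the documents do not give; and the share *s* of the variance left after own baseline that the omitted factors explain, taken as 0, 10, 20 and 40%.

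**Step 1. Approximation under perfect balance.** The true variance of the estimate is proportional to 1 − s, while the baseline-only model reports it as if it were 1. Its standard error is too large by 1/√(1 − s). With 24 − 3 = 21 degrees of freedom, t(0.95) = 1.721, and coverage is P(|T₂₁| < 1.721/√(1 − s)).

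| s | 1/√(1 − s) | Effective cut-off | Coverage |
|---|---|---|---|
| 0 | 1.000 | 1.721 | 90.0% |
| 10% | 1.054 | 1.814 | 91.6% |
| 20% | 1.118 | 1.924 | 93.2% |
| 40% | 1.291 | 2.221 | 96.3% |

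**Step 2. Simulation with realistic, imperfect balance.** Continuous-factor minimisation used 6,000 trials per setting (standard error about 0.4 points), with an 80% coin or no random element, pooled or by recruitment drive. Minimisation on factors split at the median used 4,000 trials per setting, pooled, for blood pressure. Baseline-only coverage:

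| s | Blood pressure, continuous | Blood pressure, median split | Waist or VO2 max, continuous |
|---|---|---|---|
| 10% | 90.5–91.6% | 90.4–91.2% | 91.3–91.8% |
| 20% | 91.5–93.0% | 91.8–92.1% | 92.0–93.1% |
| 40% | 94.1–95.5% | 93.6% | 94.0–95.9% |

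A further run with categorised factors gave 92–94% at 40%. At s = 0, coverage is about 90%. With the omitted factors added under continuous-factor minimisation, it is 89–91% throughout. Under a plain 12:12 random split, baseline-only coverage stays at 89.2–90.5% for shares from 0 to 50%. The excess therefore comes from minimising and then not adjusting, not from the small sample.

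**Step 3. Width after adjustment.** Adding two or three factors leaves 19 or 18 degrees of freedom, with t = 1.729 or 1.734. Under perfect balance the width ratio is (t_new/1.721) × √(1 − s). For three factors this is 1.008 × √(1 − s): +0.8% at s = 0, −4.4% at 10%, −9.9% at 20%, −21.9% at 40%. Imperfect balance costs a little more. Simulated change in width, continuous-factor minimisation:

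| s | Blood pressure | Waist or VO2 max |
|---|---|---|
| 0 | +2% to +4% | +1% to +3% |
| 10% | −2% to −4% | −3% to −4% |
| 20% | −7% to −10% | −9% to −10% |
| 40% | −20% to −22% | −21% to −22% |

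With median-split minimisation, the cost for blood pressure at s = 0 is +4% to +5%. Break-even shares are about 3–7% (blood pressure) and 2–5% (others) with continuous factors, and 8–9% (blood pressure) with median splits.

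**Step 4. The estimate itself.** At s = 20% (pooled, 80% coin, blood pressure) the SD of the estimate is 0.392 without and 0.388 with the factors. Adjustment mainly corrects the reported precision.

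**Step 5. Benefit claims.** With 21 df and a 0.2 SD threshold, benefit is P(T > (0.2 − estimate)/SE) and harm is P(T > (0.2 + estimate)/SE).

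- Estimate 0.15, SE 0.08: 0.05/0.08 = 0.625, benefit 26.9%; 0.35/0.08 = 4.375, harm 0.01%. Claim.
- Estimate 0.15, SE 0.065: 0.05/0.065 = 0.769, benefit 22.5%. No claim.
- Estimate 0.40, SE 0.22: 0.60/0.22 = 2.727, harm 0.63%. No claim.
- Estimate 0.40, SE 0.20: 0.60/0.20 = 3.0, harm 0.34%. Claim.

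A smaller standard error can remove a claim or create one. In simulation with an assumed true effect of 0.1 SD, below the threshold, and s = 40%, adjustment moved the claim rate from 29.5% to 23.4% (residual SD 0.2 of the baseline SD) or from 7.7% to 16.5% (residual SD 0.5).

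**The case against.** The strongest reply is that adjusting for own baseline is a sound choice, that any error is on the cautious side, and that its size rests on a correlation the documents never give. At a 10% share the effect is about one point of coverage, and the larger figures need a 40% share that nothing in the documents supports. All of this stands. It fixes the weight of the point but does not remove it: the omission is in the text, and the direction follows whenever the factors are prognostic beyond own baseline.

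The minimisation is also not described in detail. If the factors were categorised, the excess coverage is smaller and adjustment costs more. That stands too, and the ranges allow for it.

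Four stronger readings are tempting, and the documents support none of them.

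- *The intervals have the wrong coverage.* This is conditional. If the omitted factors add nothing beyond own baseline, the stated intervals are valid.
- *The treatment effect is biased.* It is not. The issue is the reported precision.
- *Omitting setting (club or mosque) widens the intervals in the same way.* Setting is not a listed minimisation factor. If allocation ignored it and it explains 10% or 20% of the remaining variance, baseline-only coverage is 90.2–90.3%. Over-coverage would need allocation to have balanced it, which the documents do not state.
- *Adjustment would improve the benefit claims.* The effect goes either way, and can mean more claims when the true effect is below 0.2 SD.

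A last objection is that several models with no rule for which one governs invite selective reading. That is right, and the fix has to state the rule.

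**Conclusion.** The point holds as a conditional one of modest weight. The analysis omits three minimisation factors for blood pressure and two for each of the other outcomes. If those factors predict follow-up beyond own baseline, the nominal 90% intervals are conservative: roughly 91–92% coverage at a 10% share (as low as 90.4% in individual settings), 91–93% at 20%, and 92–96% at 40%. If they do not, nothing is wrong with the intervals.

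This rests on 24 men in about equal arms, the 90% level carrying over to the health outcomes, and assumed prognostic shares and minimisation details. It is worth acting on because the intervals are meant for planning and the factors were already measured for allocation.

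**What to change.** Keep the stated baseline-only analysis. Beside it, report one linear model per health outcome of follow-up on arm, own baseline and the remaining minimisation factors:

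- blood pressure: age, baseline waist, baseline predicted VO2 max;
- waist: age, baseline predicted VO2 max;
- predicted VO2 max: age, baseline waist.

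Label it as an added analysis, because the text describes the baseline-only one as already applied. State that the magnitude-based claims stay tied to the stated analysis and that the adjusted interval is the one for planning future trials. Do not add setting on the strength of this point.

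The cost is a few lines of SAP text and one extra model run per outcome, in software already in use (SPSS) and with data already collected. If the factors carry no information, intervals at n = 24 are about 2–5% wider for blood pressure and 1–3% wider for the others. If four men were lost (an assumption, n = 20, 80% coin), the figures are about 5% and 3%. Break-even is a share of about 2–9%, depending on outcome and minimisation method. The blood pressure model has six parameters for at most 24 men, which is tight, though its simulated coverage stayed at 89–91%.
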